5.4. Subsets

The following patient characteristics will be analyzed for efficacy by subsets.

- Age [less than 5 years, 5 years or older and less than 7 years, 7 years or older].
- Mother's birth history [the first childbirth / multipara].
- Presence/absence of GHD family history.
- Twin/multiplets.
- Fetus week number [less than 33 weeks, 33 weeks or older and less than 37 weeks, 37 weeks or older].

- Silver-Russell syndrome [yes, no].
- Period from the first date of treatment with growth hormone products including Genotropin to the pubescence [less than 2 years, 2 years or longer].

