2.2. Objective

This investigation is intended to evaluate the long-term efficacy and safety of Genotropin in children with SGA dwarfism without epiphyseal closure. Responses of patients to Genotropin in relation to clinical conditions of patients, dose schedule, past history of growth hormone treatment, and other relevant factors will be investigated.

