6.4. Covariates

There are no identified or potential covariates from the clinical study or other data on the safety or efficacy of Genotropin.

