8.2.2. Patient Characteristics and Treatment History

- **Patient characteristics**

The following patient characteristics will be summarized according to 8.1 for the safety analysis set, efficacy analysis set, and eligible criteria set.

- Gender [male, female].
- Age (continuous variable) [less than 5 years, 5 years or older and less than 7 years, and 7 years or older].
- Height of father (continuous variable).
- Height of mother (continuous variable).
- Mother's birth history [the first childbirth/multipara].
- Presence/absence of GHD family history.
- Twin/multiplets.
- Childbirth procedures [normal, breech presentation, Caesarean section, multiple selection].
- Fetus week number [less than 33 weeks, 33 weeks or older and less than 37 weeks, 37 weeks or older].
- Apgar score (1 minute) (continuous variable).
- Apgar score (5 minutes) (continuous variable).

- Apgar score (10 minutes) (continuous variable).
- Birth height (continuous variable).
- Birth weight (continuous variable) [less than 1000 g, 1000 g or higher and less than 2500 g, and 2500 g or higher].
- Birth head circumference (continuous variable).
- IGF-I (continuous variable).
- IGF-I SDS (continuous variable).
- Height (continuous variable).
- Height SDS (continuous variable) [less than -2.5 SD, -2.5 SD or higher].
- Height velocity (continuous variable): $365.25 \times (\text{height at start of treatment} - \text{Height at 1 year before start of treatment}) / (\text{Height measurement date at start of treatment} - \text{Height measurement date at 1 year before start of treatment})$.
- Height velocity SDS (continuous variable) [less than 0 SD, 0 SD or higher].
- Body weight (continuous variable).
- Body weight SDS (continuous variable).
- BMI (continuous variable).
- BMI SDS (continuous variable).
- Head circumference (continuous variable).
- Bone age (male) [less than 17 years, 17 years or older].
- Bone age (female) [less than 15 years, 15 years or older].

The following number and proportion of patients will be summarized by system organ class (SOC) and preferred term (PT) in the safety analysis set.

- Details of past histories.
- Details of concurrent disease.

The following number and proportion of patients will be summarized in the safety analysis set, efficacy analysis set, and eligible criteria set.

- Details of concomitant medications.

- Details of non-drug concomitant therapies.
- Details of pretreatment drugs.
- **Treatment status of Genotropin**

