8.2.4.2. Change in Height SDS

The summary statistics of measured values of height SDS at each age will be calculated for the efficacy analysis set and eligible criteria set. The evaluation points are according to [Appendix A1.1](#) Definition of timing for visit 1. The change in height SDS will be plotted with a solid line for individual male and female patients separately, with age on the horizontal axis and height SDS on the vertical axis. The start of treatment will be indicated as ▲, pubescence as ●, and reaching adult height (near final height) as ▼. They will be plotted with a dotted line after the completion/discontinuation of treatment.

The same calculation will be performed to prepare plots in the same manner for the set of patients who reached adult height (near final height) and set of patients not reached.

The summary statistics of measured values of height SDS at each evaluation point and change from the start of Genotropin will be calculated for a set of patients who reached adult height (near final height). The 95% confidence interval of the mean of the change will be calculated. The evaluation points are according to [Appendix A1.2](#) Definition of timing for visit 2. The change in height SDS will be plotted with a solid line for individual male and female patients separately, with evaluation points on the horizontal axis and height SDS on the vertical axis. The start of treatment will be indicated as ▲, pubescence as ●, and reaching adult height (near final height) as ▼. They will be plotted with a dotted line after the completion/discontinuation of treatment.

The summary statistics of measured values of height SDS at each evaluation point and changes from the start of Genotropin will be calculated in the efficacy analysis set and eligible criteria set. The 95% confidence interval of the mean of the change will be calculated. The evaluation points are according to [Appendix A1.3](#) Definition of timing for visit 3. The change in height SDS will be plotted with a solid line for individual male and female patients separately, with evaluation points on the horizontal axis and height SDS on the vertical axis. The start of treatment will be indicated as ▲, pubescence as ●, and reaching adult height (near final height) as ▼. They will be plotted with a dotted line after the completion/discontinuation of treatment.

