8.2.4.8. Subset Analysis

A subset analysis of the change in height SDS will be performed by the factors specified in 5.4.

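### Past growth hormone treatment is named in the objective as a response factor, but no visible efficacy analysis separates GH-naive from previously GH-treated patients

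*SAP*

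**What the plan says.** The objective, in Protocol section 1 and again in SAP 2.2, is to study response in relation to clinical condition and to "dose schedule, past history of growth hormone treatment, and other relevant factors will be investigated".

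The data that define past GH treatment are collected. Protocol 5.3.1 puts both the Genotropin start date and the date of first GH therapy on the new-subject enrollment form. Protocol 6.1 lists both among the identification items. Protocol 6.2 [14] also records whether GH was given for this indication before Genotropin.

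On the analysis side:

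- SAP 5.4 opens with "The following patient characteristics will be analyzed for efficacy by subsets" and lists seven factors: age, maternal parity, family history of GHD, multiple birth, gestational age, Silver-Russell syndrome, and "Period from the first date of treatment with growth hormone products including Genotropin to the pubescence", split at 2 years.
- SAP 8.2.4.8 reads "A subset analysis of the change in height SDS will be performed by the factors specified in 5.4".
- SAP 6.4 states "There are no identified or potential covariates from the clinical study or other data on the safety or efficacy of Genotropin".
- SAP 8.2.2 tabulates "Details of pretreatment drugs" as counts and proportions.
- For the efficacy and eligible criteria sets, SAP 8.2.4.2 says "The summary statistics of measured values of height SDS at each evaluation point and changes from the start of Genotropin will be calculated". Appendix A1.2 and A1.3 place that start at the beginning of Genotropin, not of the first GH product.

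**The concern.** Of the three factors named in the objective, two reach an efficacy output. Clinical condition becomes the subsets of SAP 5.4, and dose becomes the dose-change plots of SAP 8.2.4.1 and 8.2.4.2. Past GH treatment becomes a count. The report will show how many children had earlier treatment but not how they responded.

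The omission also affects how the main tables read. Change is measured from Genotropin start. For a child who moved directly from another GH product, that baseline is already an on-treatment value, so the change does not mean what it means in a naive child. Both kinds of change go into one mean.

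The eligible criteria set does not remove the problem. Exclusions b and c in SAP 5.2 are read at Genotropin start, so for a switcher they are not pre-GH values.

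**Working it through.** The plan gives no figure to reproduce. The target of 400 (Protocol section 3; approximately 400 in SAP 2.1) comes with no SD, effect size or power.

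**Step 1: look for a split by prior GH.**

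| Place in SAP | Separates naive from pre-treated? |
|---|---|
| 5.2 and 5.3 analysis sets | No |
| 5.4 subset factors | 0 of 7 |
| 6.4 covariates | None named |
| 8.2.2 pretreatment drugs | Counts only, not crossed with response |
| 8.2.4.1 to 8.2.4.7 | No |
| 8.2.4.8 | Limited to the 5.4 factors |

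The seventh factor in 5.4 starts its clock at the first GH product of any kind. A naive child and a switcher can each have under 2 years, or 2 years or more, from first GH to puberty, so either category can hold both groups.

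**Step 2: the baseline for height velocity.** SAP 8.2.2 computes it from height at start minus "Height at 1 year before start of treatment", annualized. The interval is the year before Genotropin. For a child on another product for the m months directly before Genotropin, the share of that interval on GH is m/12:

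- 3/12 = 25%
- 6/12 = 50%
- 12/12 = 100%

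**Step 3: shift in a pooled mean.** Shift = share pre-treated × difference in mean change between the groups. Neither input is in the documents. With an assumed difference of 0.5 SDS:

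- 1%: 0.01 × 0.5 = 0.005 SDS
- 5%: 0.05 × 0.5 = 0.025 SDS
- 10%: 0.10 × 0.5 = 0.05 SDS
- 30%: 0.30 × 0.5 = 0.15 SDS

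**Step 4: what a split could show.** The 95% CI half-width for naive minus pre-treated change in height SDS is 1.96 × SD × √(1/n₁ + 1/n₂). Assumed: SD 0.5 to 1.0, the shares below, and 200 evaluable patients as a lower case beside the target of 400.

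| Share pre-treated | N = 400: groups | Half-width (SDS) | N = 200: groups | Half-width (SDS) |
|---|---|---|---|---|
| 1% | 4 vs 396 | 0.49–0.98 | 2 vs 198 | 0.70–1.39 |
| 5% | 20 vs 380 | 0.22–0.45 | 10 vs 190 | 0.32–0.64 |
| 10% | 40 vs 360 | 0.16–0.33 | 20 vs 180 | 0.23–0.46 |
| 30% | 120 vs 280 | 0.11–0.21 | 60 vs 140 | 0.15–0.30 |

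For example, 20 vs 380 with SD 0.5: 1.96 × 0.5 × √(0.05 + 0.00263) = 0.98 × 0.2294 = 0.225. At 5% or more the comparison carries some information. Near 1% the pre-treated row is 2 to 4 patients and purely descriptive.

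**The case against.** **GH history is not wholly absent.** The time-to-puberty factor counts exposure before Genotropin, and the objective does not prescribe a naive versus pre-treated split. That is fair as far as it goes. But a factor whose two categories can each contain both groups cannot say how earlier treatment relates to response.

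**Redaction.** SAP 8.2.4.9 and part of 6.2 are blacked out and may hold something relevant. This stands as a limit: those parts are not judged. The 5.4 list and the sentence in 8.2.4.8 that binds the subset analysis to it are both readable.

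**Eligibility already filters switchers.** New patients need height below -2.5 SD and pre-treatment velocity below 0 SD. Enrollment violators leave the safety set, and SAP 5.2 applies the same limits again at Genotropin start. This may reduce the number of distorted baselines but does not remove them. Ongoing patients enter by a separate route, and switchers growing below average stay in. Removing switchers who grew well on earlier GH is itself selective, which is why a footnote is needed.

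**The velocity baseline is inferred.** SAP 8.2.4.3 does not cite the formula in 8.2.2. The definition in 6.2 points to A1.3, which has no visit one year before start. True, but 8.2.2 gives the only stated definition of velocity at start.

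**Small effect, exploratory study.** At a share near 1% the pooled shift is trivial, and SAP 4.1 sets no significance level. Both points hold and limit the weight of the concern. Neither gives the objective its missing result.

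**Conclusion.** The concern holds. In the visible plan, a response factor named in the objective is collected and counted but never related to response. The pooled change-from-start tables can mix naive and on-GH baselines, most clearly for height velocity.

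The size of the distortion is unknown because the share of pre-treated patients is not documented. It is negligible if that share is very small. The shifts and half-widths shown rest on assumed shares, SDs, group difference and evaluable N. What is lost is interpretability; no test or decision rule is affected.

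**What to change.** 1. Add prior GH therapy [no / yes] to SAP 5.4, with yes meaning that the first GH date is earlier than the Genotropin start date. SAP 8.2.4.8 then reports change in height SDS by it. List any patient whose dates disagree with the item in Protocol 6.2 [14], since that item covers GH for this indication only. Where the data allow, show children on GH during the year before Genotropin apart from those off it. The protocol lists no stop date for prior GH, so this may not be possible for everyone.
2. Add GH-naive and pre-treated rows to tables already planned: height SDS, height velocity and height velocity SDS at the A1.3 points in the efficacy and eligible criteria sets, and height SDS at the A1.2 points in the adult-height set. None are needed for weight, BMI or IGF-I SDS.
3. Footnote the eligible criteria set tables: exclusions b and c in SAP 5.2 are read at Genotropin start and are not pre-GH values for switchers.

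The cost is SAP wording, one subset factor and extra table rows. The yes/no factor needs no new data. The drawback is smaller numbers per row, with pre-treated rows likely to be sparsest in the eligible criteria set.

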Meanwhile, the data collected from this investigation shall be anonymized, compiled, and used as evidence for mechanisms and causes of poor physical growth in children with SGA dwarfism without epiphyseal closure, as well as response of such children to growth hormone treatment, and to facilitate new findings and discovery concerning poor physical growth in children.

1. Objective

This investigation is intended to evaluate the long-term efficacy and safety of Genotropin in children with SGA dwarfism without epiphyseal closure. Responses of patients to Genotropin in relation to clinical conditions of patients, dose schedule, past history of growth hormone treatment, and other relevant factors will be investigated.

2. Study subjects

The indication for Genotropin in this investigation is as follows.

<Indication>

SGA (small-for-gestational age) dwarfism without epiphyseal closure

Subjects with the above disease who meet the following conditions will be enrolled in this investigation. In addition, the data in patients receiving Genotropin prior to the contract conclusion will also be included in this investigation.

- [1] Patients receiving Genotropin and consenting in writing to take part in this investigation
- [2] Newly enrolled patients who meet the following enrollment criteria
- [3] Patients who have already been enrolled in "Genotropin Special Investigation - Investigation of Genotropin long-term use in patients with SGA dwarfism without epiphyseal closure."

<Enrollment criteria>

Patients who meet all of the following criteria

- 1) Patients whose height and weight at birth are both below the 10th percentile for patients of the same gestational age, and at the same time, either body weight or height is less than -2 SD compared to patients of the same gestational age. Neonates whose body height at birth were immeasurable and thus were not measured will be evaluated with birth weight.
- 2) Eligibility for the treatment
 - [1] Patients must be not younger than 3 years.
 - [2] The current body height must be less than -2.5 SD of the standard height.
 - [3] A pre-treatment height velocity within 1 year prior to the commencement of treatment must be less than 0 SD.

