6.2. Efficacy Endpoints

- Height.
- Height SDS: $(\text{height} - \text{standard height for chronological age/gender}^2) / \text{standard deviation}$.
- Height velocity: $365.25 \times (\text{height} - \text{height of 1 year before}) / (\text{date of height measurement} - \text{date of height measurement of 1 year before})$ (height of 1 year before: Height of the previous year as used according to “[Appendix A1.3](#) Definition of timing for visit 3”).
- Height velocity SDS: $(\text{height velocity} - \text{mean height velocity for chronological age/gender}^3) / \text{standard deviation}$.

CCI

- [REDACTED]
- [REDACTED]
- [REDACTED]

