11. APPENDIXES

11.1. Appendix 1: Details of Data Extraction

A1.1 DEFINITION OF TIMING FOR VISIT 1

Timing for visit	Endpoint	Definition [allowable range]
3 years	Height Height SDS Body weight SDS BMI SDS IGF-I SDS	3 years and 0 month to 3 years and 11 months
4 years	Height Height SDS Body weight SDS BMI SDS IGF-I SDS	4 years and 0 month to 4 years and 11 months
N years	Height Height SDS Body weight SDS BMI SDS IGF-I SDS	N years and 0 month to N years and 11 months

The measured value on the latest date will be used when the same patient receives more than one measurement during the same visit.

A1.2 DEFINITION OF TIMING FOR VISIT 2

Timing for visit	Endpoint	Definition [allowable range]
Start of Genotropin therapy	Height SDS Body weight SDS BMI SDS IGF-I SDS	90 days before the first date of treatment (the start date of treatment) to the start date of treatment for this investigation
Pubescence	Height SDS Body weight SDS BMI SDS IGF-I SDS	The date evaluated as the pubescence +90 days
At reaching adult height (near final height)	Height SDS Body weight SDS BMI SDS IGF-I SDS	The date evaluated to reach adult height (near final height) +90 days

The measured value on the earliest date will be used when the same patient receives more than one measurement during the same visit.

In this regard, all the data measured after reaching adult height (near final height) will be used if plots are prepared.

A1.3 DEFINITION OF TIMING FOR VISIT 3

Timing for visit	Endpoint	Definition [allowable range]
Start of Genotropin therapy	Laboratory test parameters Height SDS Height velocity Height velocity SDS Body weight SDS BMI SDS IGF-I SDS	90 days before the first date of treatment (the start date of treatment) to the start date of treatment for this investigation
1 year later	Laboratory test parameters Height SDS Height velocity Height velocity SDS Body weight SDS BMI SDS IGF-I SDS	365 ±90 days after the start of treatment
2 years later	Laboratory test parameters Height SDS Height velocity Height velocity SDS Body weight SDS BMI SDS IGF-I SDS	730 ±90 days after the start of treatment
N years later	Laboratory test parameters Height SDS Height velocity Height velocity SDS Body weight SDS BMI SDS IGF-I SDS	365 × N ±90 days after the start of treatment
Completion of Genotropin therapy	Laboratory test parameters Height SDS Height velocity Height velocity SDS Body weight SDS BMI SDS IGF-I SDS	Final date of treatment for this investigation (completion date of treatment) ±90 days

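### Change in chronological-age height SDS is compared by gestation, which builds a small, start-age-dependent gain into the <33-week group; a corrected-age sensitivity table would expose it

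*SAP*

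**What the plan says.** SAP 6.2 defines height SDS against the "standard height for chronological age/gender". Neither document visibly gives a rule for correcting age for prematurity. SAP 5.4 lists the subset factors, including "Fetus week number [less than 33 weeks, 33 weeks or older and less than 37 weeks, 37 weeks or older" and, separately, "Age [less than 5 years, 5 years or older and less than 7 years, 7 years or older". The two are not crossed. SAP 8.2.4.8 then states: "A subset analysis of the change in height SDS will be performed by the factors specified in 5.4". It does not say at which evaluation points. SAP 8.2.4.2 gives change from start at yearly points (Appendix A1.3, for example "365 ±90 days after the start of treatment") and, for those who reach it, at adult height (Appendix A1.2).

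SAP 6.4 foresees no adjustment: "There are no identified or potential covariates from the clinical study or other data on the safety or efficacy of Genotropin". Two enrolment criteria in Protocol section 2 bear on the size of the effect: "Patients must be not younger than 3 years" and "The current body height must be less than -2.5 SD of the standard height". Gestational week at birth is a recorded item (Protocol 6.2). SAP 4.1 treats all testing as exploratory and sets no significance level.

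**The concern.** The variable that defines the subset also enters the error in the outcome. At the same chronological age, a child born at 30 weeks is 10 weeks younger since conception than one born at 40 weeks. Measured against a chronological-age reference, its height SDS is too low by roughly the growth missed in those 10 weeks divided by the reference SD. In early childhood growth is fast and the SD is small, so the shortfall is largest there. Once growth has stopped it is zero. A child who merely tracks its own corrected centile therefore shows a rising SDS.

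Relating response to patients' clinical conditions is a stated objective (Protocol section 1, SAP 2.2), and the results are meant for publication. In a descriptive plan, reading the subset differences is the whole use of the table. A finding that very preterm children respond better could be partly a property of the age scale, and the planned summaries give no means of seeing that.

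**Working it through.** The plan has no figure to reproduce. It gives no expected subset difference, no SD of change, and no derivation for the target of about 400.

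**Formula.** Let d be the weeks born early divided by 52.18 (in years), v(a) the reference growth per year at age a, SD(a) the reference SD, s the yearly rise of that SD, and z the child's corrected-age SDS. To first order, uncorrected SDS = z − d × (v(a) + z × s) / SD(a), so

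shortfall(a) = d × (v(a) + z × s) / SD(a).

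Apparent gain with no response = shortfall(start) − shortfall(end). At adult height the shortfall is 0.

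**Inputs from the documents.** Start from age 3, height below −2.5 SD, gestation groups cut at 33 and 37 weeks.

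**Assumed inputs, not in the documents.** z held at −3; s = 0.42 cm/year; a 30-week child stands for the <33-week group and a 38-week child for the ≥37-week group. Growth references (low / mid / high scenario):

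| Age | v, cm/year | SD, cm |
|---|---|---|
| 3 | 7.0 / 7.5 / 8.5 | 3.8 / 3.5 / 3.2 |
| 5 | 6.0 / 6.4 / 6.8 | 4.6 / 4.4 / 4.2 |
| 6 | 5.6 / 6.0 / 6.4 | 5.0 / 4.8 / 4.6 |
| 7 | 5.3 / 5.7 / 6.1 | 5.3 / 5.1 / 4.9 |
| 8 | 5.0 / 5.5 / 6.0 | 5.7 / 5.4 / 5.2 |
| 10 | 4.8 / 5.5 / 6.5 | 6.5 / 6.1 / 5.8 |

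**One child.** At 30 weeks, d = 10/52.18 = 0.192. At age 3, mid values: 0.192 × (7.5 − 3 × 0.42)/3.5 = 0.192 × 6.24/3.5 = 0.34 SDS. Leaving out the z × s term would give 0.192 × 7.5/3.5 = 0.41. That is too high for a child near −3 SD, who grows more slowly than the reference mean.

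**30 against 38 weeks.** The shortfall is proportional to d, so the between-child difference uses d = (10 − 2)/52.18 = 0.153. At mid values:

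- age 3: 0.153 × 6.24/3.5 = 0.273
- age 5: 0.153 × 5.14/4.4 = 0.179
- age 6: 0.153 × 4.74/4.8 = 0.151
- age 7: 0.153 × 4.44/5.1 = 0.133
- age 8: 0.153 × 4.24/5.4 = 0.120
- age 10: 0.153 × 4.24/6.1 = 0.107

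| Interval | Excess apparent gain, mid | Range over scenarios |
|---|---|---|
| 3 to 6 | 0.273 − 0.151 = 0.12 | 0.10 to 0.18 |
| 5 to 8 | 0.179 − 0.120 = 0.06 | 0.06 throughout |
| 7 to 10 | 0.133 − 0.107 = 0.03 | 0.01 to 0.03 |
| 3 to adult | 0.273 − 0 = 0.27 | 0.23 to 0.35 |
| 7 to adult | 0.133 − 0 = 0.13 | 0.12 to 0.15 |

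**Pooled over start ages.** The fetus-week groups mix all start ages. If, purely for illustration, equal thirds started at 3, 5 and 7, the three-year excess would be (0.12 + 0.06 + 0.03)/3 = 0.07.

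**Against sampling error.** Assume 40 to 80 children below 33 weeks, 250 at term, and an SD of change of 0.5 to 0.7. The 95% half-width for a difference is 1.96 × SD × √(1/n₁ + 1/n₂): from 1.96 × 0.5 × √(1/80 + 1/250) = 0.13 to 1.96 × 0.7 × √(1/40 + 1/250) = 0.23. The mid three-year excesses (0.12, 0.06, 0.03) all lie below this range.

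**The case against.** The strongest reply is that the size is entirely assumed. The documents contain no growth-reference values, no subset counts and no SD of change. That stands, and it is why the result is given as a range by start age. The direction over these intervals does not depend on which scenario is used.

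Second, the effect is small for many children. SAP 5.4 has a stratum starting at 7 or older, where three years of follow-up give only 0.01 to 0.03. This also stands, so the age-3 figure should not be read as the bias of the whole <33-week group.

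Third, a reader might infer that the bias grows steadily with follow-up. The documents do not support that. The shortfall can widen for a time during the pubertal growth spurt, which the calculation does not model. Only the end point, zero at adult height, is fixed. Nor do the documents show that children starting at 3 will reach adult height in a three-year, extendable investigation, even with the earlier data on ongoing patients that SAP 2.1 brings in. True catch-up also makes the artefact slightly smaller than the constant −3 SD case.

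Fourth, a reader might infer that the artefact is as large as the subset's uncertainty. That would set a between-group excess against a one-group interval. Against the interval for a difference it is usually smaller. The exceptions are the upper scenarios from age 3 and the early-start-to-adult result, where fewer children would contribute and the interval would be wider.

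Fifth, chronological age is the usual convention at these ages, and the analysis is one of seven exploratory factors with no decision rule. Both are true. They argue for a sensitivity table and against any change of endpoint.

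Finally, some endpoints in SAP 6.2 and all of 8.2.4.9 are blacked out, so the absence of a correction can be asserted only for the visible text. The visible definition of height SDS is nevertheless complete in itself.

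**Conclusion.** The point holds as a modest bias of known direction in one exploratory comparison. From start to any prepubertal yearly point, and from start to adult height, the <33-week group's change in height SDS includes a gain that owes nothing to Genotropin. Its size depends mainly on age at start and is about a tenth of an SDS or less over three years at mid values. It is larger only for an early start followed to adult height. These sizes rest on the assumed references, on z = −3, and on 30 and 38 weeks as typical of their groups.

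A reader might go further and conclude that the chronological-age height SDS is an error, or that the overall efficacy result is inflated. The documents support neither. The overall mean is hardly affected, and no hypothesis or decision in the plan turns on this subset. What is missing is a way to tell the artefact from a difference in response.

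**What to change.** In SAP 8.2.4.8, for the fetus-week factor only, add a sensitivity table of change in height SDS computed on corrected age: chronological age minus (40 − fetus weeks)/52 years, at start and at each evaluation point. Restrict it to patients whose fetus week is recorded. Protocol section 6 marks that item under Booklet 01 and ongoing patients begin on Booklet 02 (5.5.2), so for them it depends on data from the earlier investigation. Put the table beside the planned chronological-age result, preferably also by the existing age-at-start groups, and discuss any difference by gestation in the light of both. A child whose corrected SDS stays constant shows no gain in the new table, by construction.

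The cost is one sentence in the SAP and one extra table, with no new data collection. The downside is that correction at these ages is not the usual convention, so the table must be labelled as sensitivity only. It replaces nothing and adds no decision criterion.
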